16-May-2011

**LipaCreon® Granules 300 mg Sachet
& LipaCreon® Capsules 150 mg**

Protocol for Special Investigation (All cases)

- Special Investigation (All cases) of LipaCreon in patients with pancreatic exocrine insufficiency due to Cystic Fibrosis -**

Protocol No. : P12-893

LipaCreon® Granules 300 mg Sachet & LipaCreon® Capsules 150 mg
Protocol for Special Investigation (All cases)

- Special Investigation (All cases) of LipaCreon in patients with pancreatic exocrine insufficiency due to Cystic Fibrosis -

1. Objective of registry

The registry aims at collecting the information related to the safety and efficacy in the pancreatic exocrine insufficiency (PEI) patients due to cystic fibrosis (CF) receiving the treatment with LipaCreon in order to obtain the information for the effective and safe use of LipaCreon.

2. Planned number of cases for the registry and justification

Planned number of cases: All the cases

Justification:

The number of enrolled patients in the domestic clinical studies was few, and prompt collection of sufficient information is necessary. And the nationwide CF patient number who was reported during the whole year of 2004, was 13, and the total patients population of CF patient for 10 years from 1995 was 38*. The number of CF patients in Japan is extremely few. From this background, the target of the study is all the cases treated with LipaCreon.

*) The Research Result relating to the intractable pancreatic diseases conducted by MHLW Scientific Research Subsidiary Intractable Disease Research Enterprises during 2005 to 2007: 205-215, 2008

3. Target patients of registry

Patients with PEI attributable to primary disease of CF.

<Indications>

Replacement of pancreatic digestive enzymes in PEI

<Precautions for use related to indications>

Administer LipaCreon to patients with having symptoms of steatorrhea or other symptomatology due to PEI because of underlying diseases of chronic pancreatitis (CP) during non-compensatory period, pancreatectomy (PY) and pancreatic CF, etc.

<Contraindication>

- (1) Patients with a history of hypersensitivity to the ingredient of LipaCreon.
- (2) Patients with a history of hypersensitivity to porcine protein.

4. Dosage & administration method

Usually, 600 mg/meal of LipaCreon should be administered t.i.d. orally, immediately after meal.

In addition, the dose should be adjusted as needed based on patient's condition.

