If dosage increase from usual daily dosage (1800mg) is to be done during the observation period or follow-up period, perform measurement of nutritious assessment items and monitor the symptoms relating to pancreatic exocrine insufficiency before the dosage increase. (Please refer 8. Items of registry (7) and (8))

[Precautions related to dosage and administration method]

In regarding to the adjustment of dosage and administration, age, weight, volume of meal, dietary and frequency of meal, etc. should be considered.

[Important Precaution]

In overseas, there were reports of stenosis of ileocecal area and colon (fibrosing colonopathy) in CF patients who have been administrated with high dosage of pancreatin products. So, careful observation should be provided and if any abnormality or change of abdominal symptom was found, appropriate action should be taken. Especially for patients with PEI due to CF, careful observation is necessary if patient is administered over 150 mg (equivalent to 1/2 sachet or one capsule) per kg body weight per day of Pancrelipase.

5. Number of planned institutions for registry by department

The registry will take place in departments of pediatric, internal medicine, digestive organs, and gastroenterology, etc. The number of the planned institutions is unknown because the contract will be signed after confirming the CF patient's availability in that institution.

6. Method of registry

(1) Request/Contract of the Registry

The target medical institutions are where LipaCreon is to be adapted/delivered and any CF patient is under or planning to be provided treatment. Medical Representative in charge of each medical institution explains to the doctors and relating people in charge, the purpose, target subjects and method of this registry sufficiently. In case the acceptance for the participation to this registry was obtained, he/she takes actions for the contract. The contract is to be signed between the head of medical institution and the sponsor in writing.

(2) Selection of target patients and registration

- 1) Prospective registry method is employed. It is an all cases registry.
- 2) Doctor in charge of this registry registers the patient is under or planning to be provided treatment by LipaCreon, by sending facsimile the registration form to the registration center. The registration form should include following items :
 - ① Patient ID No., ② Sex, ③ Date of birth or age,
 - ④ Inpatient/outpatient classification,

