2.3. Definitions of Patient Demographic Factors and Indicators of Treatment Status

No	Patient demographic factor	Description
1	Sex	Male, female, unknown/unspecified
2	Pregnancy status	Not pregnant, currently pregnant, unknown/unspecified
3	Breastfeeding status	Not breastfeeding, currently breastfeeding, unknown/unspecified
4	Age category-1	<15 years old, ≥15 years old, unknown/unspecified
5	Age category-2	<6 years old, ≥6 years old and <12 years old, ≥12 years old and <18 years old, ≥18 years old, unknown/unspecified
6	Age	Actual value
7	Body height category-1	<140 cm, ≥140 cm and <150 cm, ≥150 cm and <160 cm, ≥160 cm and <170 cm, ≥170 cm and <180 cm, ≥180 cm, unknown/unspecified
8	Body height	Actual value
9	Body weight category-1	<30 kg, ≥30 kg and <40 kg, ≥40 kg and <50 kg, ≥50 kg and <60 kg, ≥60 kg and <70 kg, ≥70 kg and <80 kg, ≥80 kg, unknown/unspecified
10	Body weight	Actual value
11	BMI category-1	<18.5, ≥18.5 and <25, ≥25, unknown/unspecified
12	BMI	Actual value Body weight / (Body height/100)**2 The value will be indicated to two decimal places rounded from three decimals.
13	Inpatient/outpatient category	Inpatient, outpatient, unknown/unspecified
14	Presence or absence of concurrent diseases	Absent, present, unknown/unspecified
15	Presence or absence of concurrent hepatic impairment	Absent, present, unknown/unspecified
16	Presence or absence of concurrent renal impairment	Absent, present, unknown/unspecified
17	Presence or absence of concurrent respiratory disease	Absent, present, unknown/unspecified
18	Presence or absence of other concurrent diseases	Absent, present, unknown/unspecified
19	Presence or absence of previous diseases	Absent, present, unknown/unspecified
20	Presence or absence of allergy history	Absent, present, unknown/unspecified
21	Presence or absence of previous drugs	Absent, present, unknown/unspecified
22	Presence or absence of concomitant digestive enzyme preparations	Absent, present, unknown/unspecified
No	Indicator of treatment status	Description
23	Dosage form	Granule, capsule, granule + capsule, unknown/unspecified

No	Patient demographic factor	Description

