36	Initial daily dose (mg/day)	The initial daily dose will be determined based on the daily dose on the start date of treatment with Lipacreen. <900, 900, >900 and <1800, 1800, >1800, unknown/unspecified

No	Patient demographic factor	Description
37	Mean daily dose (safety) (mg/day)	
The mean daily dose will be determined based on the mean daily dose (safety). <900, 900, >900 and <1800, 1800, >1800, unknown/unspecified
 
The mean daily dose for each dose observation period will be determined based on the mean daily doses during the individual periods shown below.
 
Dose observation periods:
 
 At the start of treatment: Day 1 At Week 2: Day 2 to Day 14 At Week 4: Day 15 to Day 28 At Week 8: Day 29 to Day 56 At Week 16: Day 57 to Day 112 At Week 24: Day 113 to Day 168 At Week 32: Day 169 to Day 224 At Week 40: Day 225 to Day 280 At Week 48: Day 281 to Day 336 At Week 52: Day 337 to Day 364 At Year 2: Day 365 to Day 728 At Year 3: Day 729 to Day 1092 At Year 4: Day 1093 to Day 1456 At Year 5: Day 1457 to Day 1820 At Year 6: Day 1821 to Day 2184 At Year 7: Day 2185 to Day 2400

No	Indicator of treatment status	Description
38	Mean daily dose (effectiveness rate) (mg/day)	
The mean daily dose will be determined based on the mean daily dose (effectiveness rate). <900, 900, >900 and <1800, 1800, >1800, unknown/unspecified
 
The mean daily dose for each dose observation period will be determined based on the mean daily doses during the individual periods shown below.
 
Dose observation periods:
 
 At the start of treatment: Day 1 At Week 2: Day 2 to Day 14 At Week 4: Day 15 to Day 28 At Week 8: Day 29 to Day 56 At Week 16: Day 57 to Day 112 At Week 24: Day 113 to Day 168 At Week 32: Day 169 to Day 224 At Week 40: Day 225 to Day 280 At Week 48: Day 281 to Day 336 At Week 52: Day 337 to Day 364

No	Indicator of treatment status	Description
39	Maximum daily dose (safety) (mg/day)	
The maximum daily dose will be determined based on the maximum value of the daily dose during the duration of use of Lipacreon (safety). <900, 900, >900 and <1800, 1800, >1800, unknown/unspecified
 
In the summarization for the occurrence status of adverse events and adverse drug reactions, the maximum daily dose in a patient experiencing an adverse event or adverse drug reaction will be determined based on the maximum daily dose until the time of initial onset of the event.

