4.3.3.1. Changes over time in the symptoms of exocrine pancreatic insufficiency

For patients included in the effectiveness analysis or patients included in the effectiveness analysis (patients completing the 52-week treatment), the changes over time in the symptoms of exocrine pancreatic insufficiency by evaluation time point will be displayed.

For steatorrhea, diarrhea, bad stool odor, anorexia, and abdominal bloating, the number of patients with or without each symptom and by pattern of change from the start of treatment will be calculated. In addition, a McNamara test will be used to confirm the equivalence in the patterns of change.

Summary statistics for the actual measurement values of the frequency of defecation by evaluation time point and changes in the frequency of defecation from the start of treatment will be calculated. In addition, a paired t-test will be used to identify the presence or absence of any change in the frequency of defecation from the start of treatment (Table 3.3.1.1, Table 3.3.1.2).

No	Item name	Description
1	Symptoms of exocrine pancreatic insufficiency	Discrete data: Steatorrhea, diarrhea, bad stool odor, anorexia, abdominal bloating Continuous data: Frequency of defecation (times/day)

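### SAP 3.6 counts the usual 1800 mg/day as a dose increase, Table 5.2.1.2 omits diarrhea, and no described table sets adverse drug reactions against the protocol's 150 mg/kg/day caution mark

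*SAP*

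**What the plan says.** Protocol 4 gives the usual dose: "Usually, 600 mg/meal of LipaCreon should be administered t.i.d. orally, immediately after meal". It asks for nutrition and symptom assessments beforehand "If dosage increase from usual daily dosage (1800mg) is to be done during the observation period or follow-up period". Its precaution names fibrosing colonopathy in CF patients on high-dose pancreatin and tells clinicians that "careful observation should be provided and if any abnormality or change of abdominal symptom was found, appropriate action should be taken". For CF it adds that "careful observation is necessary if patient is administered over 150 mg (equivalent to 1/2 sachet or one capsule) per kg body weight per day".

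SAP 3.6 makes the assessment before a dose increase an evaluation time point, with a window from 28 days before the increase up to its start date. Footnote 2 treats any administered dose of at least 1800 mg/day as an increase. SAP 4.3.3.1 then says that, for the discrete symptoms, "the number of patients with or without each symptom and by pattern of change from the start of treatment will be calculated".

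All SAP dose variables are in mg or mg/day. Initial, mean, maximum and last daily dose share the classes "<900, 900, >900 and <1800, 1800, >1800, unknown/unspecified". Body weight is a separate factor, with classes starting "<30 kg, ≥30 kg and <40 kg, ≥40 kg and <50 kg, ≥50 kg and <60 kg". Table 2.3.1.1 (SAP 4.2.3.1) takes the SAP 2.3 factors one at a time and tests each by Fisher's exact or Kruskal-Wallis test.

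**The concern.** Two items are wrong as written. Footnote 2 turns the unchanged usual dose into a dose increase, which is not what the protocol means, and so puts the wrong patients and dates into the before-increase summaries. Table 5.2.1.2, the patient-level listing of symptoms, drops one of the protocol's six symptoms.

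The third item is a missed opportunity. The protocol states its bowel-safety caution per kg of body weight. The registry collects dose and weight, but the SAP never divides one by the other. Table 2.3.1.1 therefore cannot show whether adverse drug reactions are more frequent above 150 mg/kg/day. The mg/day classes can even order two patients the opposite way from the protocol's mark.

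**Working it through.** **1. Usual dose.** 600 mg × 3 meals = 1800 mg/day, which reproduces the protocol's own figure. The mark's equivalence also holds: half of a 300 mg sachet = 150 mg = one capsule.

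**2. Footnote 2 against Protocol 4** (illustrative dose courses).

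| Course (mg/day) | Footnote 2, read literally | Protocol 4 |
|---|---|---|
| Starts and stays at 1800 | Increase, dated Day 1 | No increase |
| 900, then 1800 | Increase | No assessment required |
| 1800, then 3600 | Threshold already met on Day 1 | Increase at the step to 3600 |

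In the first row the before-increase window runs from 28 days before Day 1 to Day 1. That lies inside the baseline window, which is everything up to Day 1. Both windows take the value nearest Day 1, so a baseline value from those 28 days serves as both, and its change from the start is zero by construction.

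**3. Diarrhea.** Protocol 8(8) lists steatorrhea, defecation frequency, diarrhea, stool odor, appetite loss and abdominal distention. SAP 4.3.3.1 covers all six. Table 5.2.1.2 has five: diarrhea is missing from both its item row and its unit row.

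**4. The mark in mg/day** = 150 × weight (illustrative weights).

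| Weight (kg) | Mark (mg/day) | 1800 mg/day expressed per kg |
|---|---|---|
| 6 | 900 | 300 |
| 10 | 1500 | 180 |
| 12 | 1800 | 150 |
| 20 | 3000 | 90 |
| 30 | 4500 | 60 |
| 60 | 9000 | 30 |

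Above 12 kg the mark falls inside the open class above 1800, which therefore mixes doses on both sides of it. An example of reversed order: a 10 kg child on 1800 mg/day receives 180 mg/kg/day and sits in class 1800. A 60 kg adult on 3600 mg/day receives 3600/60 = 60 mg/kg/day and sits in the top class.

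**5. Would crossing dose with weight class help?** Five dose classes by seven weight classes give 35 cells.
- From 30 kg up, doses to 1800 give at most 1800/30 = 60 mg/kg/day. So 4 × 6 = 24 cells lie wholly below the mark.
- The top dose class is mixed in the 6 weight classes from 30 kg up, though only doses above 4500 mg/day can exceed the mark there.
- Under 30 kg all 5 cells are mixed, because weight has no lower bound. The two lowest dose classes exceed the mark only under 6 kg.

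That gives 24 below, 11 mixed and 0 wholly above. The SAP does not plan this cross-table; the count shows only that existing classes could not replace a per-kg dose.

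**6. Which weight to use.** Children grow: 3000 mg/day is 200, 150 and 120 mg/kg/day at 15, 20 and 25 kg. The latest weight is the sensible choice, but it can be 52 − 24 = 28 weeks old between Weeks 24 and 52, and about a year old afterwards. A pre-increase weight is required only for increases from 1800 mg/day, so a 10 kg child can pass its mark of 1500 mg/day without one.

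**The case against.** The 150 mg/kg/day text is a precaution for prescribers. Protocol 9 promises adverse drug reactions by patient background, which the SAP delivers. Change from the start of treatment is the normal reference in an effectiveness section, and symptoms are also shown at each time point. New abdominal disorders are recorded as adverse events or CF-attributed events, and both are listed. The population is tiny (Protocol 2 cites 13 patients in 2004 and 38 over ten years), and Table 5.2.1.1 (dated doses) and Table 5.2.1.2 (weights) allow mg/kg/day to be worked out by hand. SAP 5.1 permits further analyses. The small-child example is invented, and nobody may exceed the mark.

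Most of this stands, and it makes the per-kg dose an improvement rather than a correction. It does not rescue footnote 2 or the missing diarrhea item. Rebuilding by hand is also awkward: Table 2.1.5.1 has no body weight, so dose, weight and event must be joined across listings. Small children are foreseen, since SAP 2.3 has an age class under 6 years and Protocol 5 names pediatric departments.

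A reader might see SAP 4.2.2.2 as a conflicting definition of an increase. It classifies the dose pattern over the whole course for Table 2.2.2, and does not conflict with footnote 2.

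**Conclusion.** Footnote 2 and the diarrhea omission are errors of definition and listing, small and certain. Footnote 2 affects the before-increase summaries; how many patients it misplaces depends on how many took exactly 1800 mg/day, which the documents do not give. The absent mg/kg/day dose is a gap worth closing cheaply, because the mg/day classes cannot isolate patients above the protocol's own mark.

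Three stronger readings are tempting and unsupported:
- That the SAP breaks a protocol commitment. Protocol 9 plans no analysis by mg/kg/day.
- That the change-from-start analysis in SAP 4.3.3.1 is wrong. It is a legitimate effectiveness comparison that was not designed to look at dose.
- That the high-dose risk cannot be examined at all. The listings permit it by hand, though not against diarrhea as a symptom item. Attached Forms 3 and 16, specified separately, might show more.

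The weights and doses in the examples are assumptions. The number of patients above 150 mg/kg/day is unknown and could be zero.

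**What to change.** 1. **SAP 3.6, footnote 2:** define a dose increase as an increase in daily dose to above 1800 mg/day.
2. **Table 5.2.1.2:** add diarrhea to the item and unit rows.
3. **Per-kg dose:** derive daily dose divided by the latest body weight on or before that date, and show the date of that weight. Show mg/kg/day at onset in Table 2.1.5.1.
4. **One descriptive table:** maximum mg/kg/day (at most 150, above 150, unknown) with adverse drug reaction counts. State that it is exempt from the SAP 4.2.3.1 tests, since any factor simply added to SAP 2.3 would receive a p-value. If it follows the maximum-dose rule in SAP 2.3 No. 39, exposure in patients with a reaction "will be determined based on the maximum daily dose until the time of initial onset of the event", while other patients contribute their whole course. The split must therefore not be read as a test of harm.
5. **Optional:** a descriptive safety-set listing of abdominal distention, diarrhea or appetite loss that goes from absent to present since the previous assessment. Show daily dose, mg/kg/day and any rise in daily dose since that assessment. Some entries will be ordinary pancreatic insufficiency.

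The cost is SAP wording, one derived variable, one small table and, if wanted, one listing. No new data and no change in care are needed.

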3.2. Testing

When any test is applied, a two-sided level of significance of 5% will be used without correction for continuity or adjustment of multiplicity.

P-values will be displayed with two asterisks (**) when being larger than 0 (zero) and less than 0.01 and with one asterisk (*) when being greater than or equal to 0.01 and less than 0.05. For any unknown/unspecified value, its frequency will be displayed in the tabulation, but it will not be included in the calculation for testing.

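### The SAP gives a McNemar test the task of confirming equivalence, which a test of difference without a margin or interval cannot do

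*SAP*

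**What the plan says.** SAP section 4.3.3.1 covers five binary symptoms and one continuous one. For the binary symptoms it plans a tabulation: "For steatorrhea, diarrhea, bad stool odor, anorexia, and abdominal bloating, the number of patients with or without each symptom and by pattern of change", where change is measured against baseline. It then adds that "a McNamara test will be used to confirm the equivalence in the patterns of change". For the continuous symptom the same section says that "a paired t-test will be used to identify the presence or absence of any change in the frequency of defecation from the start of treatment". Section 4.3.2.1 describes the paired t-test for the nutritional endpoints in the same way, as a search for change.

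SAP section 3.2 sets the testing rule: "a two-sided level of significance of 5% will be used without correction for continuity or adjustment of multiplicity". It marks p-values below 0.05 and below 0.01 with asterisks and leaves unknown values out of the tests. It says nothing about how to read a p-value of 0.05 or more.

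Protocol section 2 fixes no sample size ("Planned number of cases: All the cases"). As background it says that the number of patients reported in 2004 "was 13, and the total patients population of CF patient for 10 years from 1995 was 38", and comments that "The number of CF patients in Japan is extremely few".

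Neither document gives an equivalence margin, a confidence interval for the change in symptom prevalence, or an expected rate of symptom change.

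**The concern.** A McNemar test asks whether the number of patients who lost a symptom differs from the number who gained it. Its null hypothesis is that the two are equally likely. A small p-value is evidence of change. A large one is only a failure to find change: it can arise because little changed or because there were too few discordant patients to tell. Confirming equivalence needs something else, namely a margin stated in advance and an interval that lies inside it.

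The stated purpose is therefore one that the test cannot serve, and it runs opposite to the purpose given for the paired t-tests beside it, with no reason offered. What is at stake is how the symptom tables (Tables 3.3.1.1 and 3.3.1.2, both listed for the re-examination) are read. Taken literally, the sentence lets an inconclusive comparison be described as a confirmed absence of change, whether the symptom had in fact improved or worsened.

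**Working it through.** The plan states no power, margin or effect size for this test, so there is no figure of its own to reproduce. The check has three parts.

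**Inputs.** From SAP section 3.2: two-sided 5%, no continuity correction. From protocol section 2: n = 13 and n = 38, used as illustrative sizes because they are historical national counts. Assumptions, not in the documents: n = 20 and n = 30, and all rates of losing or gaining a symptom.

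**1. What the test needs to reach significance.** Let b be the number of patients who lose the symptom and c the number who gain it. The statistic is (b − c)²/(b + c), compared with 3.84.
- 3 versus 0: 9/3 = 3.00, not significant.
- 4 versus 0: 16/4 = 4.00, significant.

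So at least four discordant patients, all in one direction, are needed. With fewer, the result is non-significant whatever happened.

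**2. What a non-significant result can hide.** The paired difference is (b − c)/n, with Wald standard error √[(b + c) − (b − c)²/n]/n.
- n = 13, b = 6, c = 2: statistic 16/8 = 2.00, p = 0.157. Difference 4/13 = 0.31; standard error √(8 − 16/13)/13 = 0.200; 95% interval −0.08 to 0.70.
- n = 38, b = 6, c = 2: same statistic and p-value. Difference 4/38 = 0.11; standard error √(8 − 16/38)/38 = 0.072; 95% interval −0.04 to 0.25.
- n = 13, b = 2, c = 2: statistic 0, p = 1. Difference 0; standard error √4/13 = 0.154; 95% interval −0.30 to 0.30.

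The third case is the most even split possible, yet changes of up to 30 points in either direction remain compatible with the data. The p-value alone does not show this; the interval does. The Wald interval is used here only because it can be checked by hand.

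**3. How often a real change is missed.** The probability of a non-significant result is one minus the sum, over all (b, c) with (b − c)²/(b + c) ≥ 3.84, of the trinomial probability n!/[b! c! (n − b − c)!] · p_lost^b · p_gained^c · (1 − p_lost − p_gained)^(n − b − c).

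| Assumed lost / gained | True net change | n=13 | n=20 | n=30 | n=38 |
|---|---|---|---|---|---|
| 20% / 5% | 15 points | 85% | 74% | 63% | 55% |
| 30% / 5% | 25 points | 66% | 51% | 33% | 21% |
| 40% / 5% | 35 points | 48% | 30% | 12% | 5% |

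The answer depends heavily on the assumed rates. Modest changes are missed more often than not across the whole range of n; a large change is missed rarely at n = 30 or more. Because unknown values are left out of testing, the number of pairs cannot exceed the number of patients and may be smaller.

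**The case against.** The strongest reply is that this is loose wording rather than a planned equivalence claim. The section is about changes over time, the neighbouring t-tests look for change, and the phrase may be an imprecise rendering of McNemar's null hypothesis, that losing and gaining the symptom are equally likely. The misspelt test name points the same way. This cannot be settled from the documents, but it is at least as plausible as the literal reading. It does not rescue the sentence, because the purpose as written is still wrong; it does make the correction easier.

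A reader might go further and infer that every non-significant result will be reported as confirmed equivalence. The documents do not say that. SAP section 3.2 only attaches asterisks to small p-values and gives no label to the rest.

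A reader might also infer that most of these tests will be non-significant. That is not supported either: the documents give no symptom rates, protocol section 2 sets no sample size, 13 and 38 are neither a forecast nor a cap, and the table above shows that a larger true change would usually be detected at n = 20 or more.

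Two further points stand. The counts by pattern of change already planned in section 4.3.3.1 contain the discordant counts, so a marked shift would be visible next to the p-value. Section 4.5.2.1 also lists individual symptom data by time point (Table 5.2.1.2), although diarrhea is missing from that list. And this is a survey without a stated primary hypothesis; no decision in the plan hangs on these p-values.

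**Conclusion.** The point holds as a defect of stated purpose. A test of difference with no margin and no interval cannot confirm equivalence, whatever the number of patients; that conclusion needs no assumption. It is wrong as written and inconsistent with the parallel t-tests in sections 4.3.2.1 and 4.3.3.1.

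How much it matters in practice does rest on assumptions. Over n = 13 to 38, the chance that a real change goes undetected runs from 85% down to 55% for a 15-point net change, from 66% to 21% for 25 points, and from 48% to 5% for 35 points. Small numbers make misreading more likely, but they are not the source of the error. The effect is on how the symptom results may be interpreted; the planned counts themselves are sound.

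**What to change.** Replace the sentence in SAP section 4.3.3.1 with: *A McNemar test will be used to test for change from the start of treatment; p ≥ 0.05 will not be interpreted as equivalence or no change.*

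In Tables 3.3.1.1 and 3.3.1.2, next to the pattern-of-change counts already planned, add the paired difference in symptom prevalence with a 95% confidence interval by a method suited to small samples.

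If equivalence really is intended, a margin and an interval-based rule must be specified before the data are analysed.

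The cost is one sentence of SAP text and one more interval per symptom row. No new data are needed.
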